6.8. Capture of cases of measles and rubella (Amended: 09 August 2016)

At each study visit subsequent to the first vaccination, it must be verified if the subject has experienced or is experiencing measles or rubella. If it is the case, the condition(s) must be recorded in the eCRF.

During the course of the study, any clinical presentation compatible with measles, rubella or YF will be captured as AE or SAE as appropriate and confirmatory serology tests should be performed to identify cases of vaccine failure.

7. HEALTH ECONOMICS

Not applicable.

8. SAFETY

The investigator or site staff is/are responsible for the detection, documentation and reporting of events meeting the criteria and definition of an AE or SAE as provided in this protocol.

Each subject's parent(s)/LAR(s) will be instructed to contact the investigator immediately should they/the subject manifest any signs or symptoms they perceive as serious.

8.1. Safety definitions

8.1.1. Definition of an adverse event

An AE is any untoward medical occurrence in a clinical investigation subject, temporally associated with the use of a medicinal product, whether or not considered related to the medicinal product.

An AE can therefore be any unfavorable and unintended sign (including an abnormal laboratory finding), symptom, or disease (new or exacerbated) temporally associated with the use of a medicinal product. For marketed medicinal products, this also includes failure to produce expected benefits (i.e. lack of efficacy), abuse or misuse.

Examples of an AE include:

- Significant or unexpected worsening or exacerbation of the condition/indication under study.
- Exacerbation of a chronic or intermittent pre-existing condition including either an increase in frequency and/or intensity of the condition.
- New conditions detected or diagnosed after investigational vaccine(s)/product(s) administration even though they may have been present prior to the start of the study.
- Signs, symptoms, or the clinical sequelae of a suspected interaction.
- Signs, symptoms, or the clinical sequelae of a suspected overdose of either investigational vaccine(s)/product(s) or a concurrent medication (overdose per se should not be reported as an AE/SAE).
- Signs, symptoms temporally associated with vaccine administration.
- Significant failure of expected pharmacological or biological action.
- Pre- or post-treatment events that occur as a result of protocol-mandated procedures (i.e. invasive procedures, modification of subject's previous therapeutic regimen).

AEs to be recorded as endpoints (solicited AEs) are described in Section 8.1.3. All other AEs will be recorded as UNSOLICITED AEs.

Examples of an AE DO NOT include:

- Medical or surgical procedures (e.g. endoscopy, appendectomy); the condition that leads to the procedure is an AE/SAE.
- Situations where an untoward medical occurrence did not occur (e.g. social and/or convenience admission to a hospital, admission for routine examination).
- Anticipated day-to-day fluctuations of pre-existing disease(s) or condition(s) present or detected at the start of the study that do not worsen.
- Pre-existing conditions or signs and/or symptoms present in a subject prior to the first study vaccination. These events will be recorded in the medical history section of the eCRF.

8.1.2. Definition of a serious adverse event

A SAE is any untoward medical occurrence that:

- a. Results in death,
- b. Is life-threatening,

Note: The term 'life-threatening' in the definition of 'serious' refers to an event in which the subject was at risk of death at the time of the event. It does not refer to an event, which hypothetically might have caused death, had it been more severe.

- c. Requires hospitalization or prolongation of existing hospitalization,

Note: In general, hospitalization signifies that the subject has been admitted at the hospital or emergency ward for observation and/or treatment that would not have been appropriate in the physician's office or in an out-patient setting. Complications that occur during hospitalization are also considered AEs. If a complication prolongs hospitalization or fulfills any other serious criteria, the event will also be considered serious. When in doubt as to whether 'hospitalization' occurred or was necessary, the AE should be considered serious.

Hospitalization for elective treatment of a pre-existing condition (known or diagnosed prior to informed consent signature) that did not worsen from baseline is NOT considered an AE.

- d. Results in disability/incapacity, OR

Note: The term disability means a substantial disruption of a person's ability to conduct normal life functions. This definition is not intended to include experiences of relatively minor medical significance such as uncomplicated headache, nausea, vomiting, diarrhea, influenza like illness, and accidental trauma (e.g. sprained ankle) which may interfere or prevent everyday life functions but do not constitute a substantial disruption.

Medical or scientific judgment should be exercised in deciding whether reporting is appropriate in other situations, such as important medical events that may not be immediately life-threatening or result in death or hospitalization but may jeopardize the subject or may require medical or surgical intervention to prevent one of the other

outcomes listed in the above definition. These should also be considered serious. Examples of such events are invasive or malignant cancers, intensive treatment in an emergency room or at home for allergic bronchospasm, blood dyscrasias or convulsions that do not result in hospitalization.

In this study, the following AEs of specific interest (pIMDs, meningitis and seizure within 30 or 42 days of vaccination) will be reported as SAEs (see also Section 8.1.5).

8.1.3. **Solicited adverse events**

8.1.3.1. **Solicited local (injection-site) adverse events**

The following local (injection-site) AEs will be solicited:

Table 13 Solicited local adverse events

Pain at injection site
Redness* at injection site
Swelling at injection site

* In case the principal investigator or designate is unable to determine the extent of redness on darkly pigmented skin, it will be reported as uninterpretable in the eCRF

8.1.3.2. **Solicited general adverse events**

The following general AEs will be solicited:

Table 14 Solicited general adverse events

Drowsiness
Fever
Irritability/Fussiness
Loss of appetite
Measles/rubella-like rash*

* To be confirmed by physician

Note: Temperature will be recorded daily. Should additional temperature measurements be performed at other times of day, the highest temperature will be recorded in the eCRF.

8.1.4. **Clinical laboratory parameters and other abnormal assessments qualifying as adverse events or serious adverse events**

In absence of diagnosis, abnormal laboratory findings (e.g. clinical chemistry, hematology, urinalysis) or other abnormal assessments that are judged by the investigator to be clinically significant will be recorded as AE or SAE if they meet the definition of an AE or SAE (refer to Sections 8.1.1 and 8.1.2). Clinically significant abnormal laboratory findings or other abnormal assessments that are present at baseline and significantly worsen following the start of the study will also be reported as AEs or SAEs.

The investigator will exercise his or her medical and scientific judgment in deciding whether an abnormal laboratory finding or other abnormal assessment is clinically significant.

8.1.5. Adverse events of specific interest

All adverse events of specific interest described below will be reported as SAEs.

8.1.5.1. Potential immune-mediated diseases

pIMDs are a subset of AEs that include autoimmune diseases and other inflammatory and/or neurologic disorders of interest which may or may not have an autoimmune etiology. AEs that need to be recorded and reported as pIMDs include those listed in [Table 15](#). pIMD will be reported as SAEs.

However, the investigator will exercise his/her medical and scientific judgment in deciding whether other diseases have an autoimmune origin (i.e. pathophysiology involving systemic or organ-specific pathogenic autoantibodies) and should also be recorded as a pIMD.

Table 15 List of potential immune-mediated diseases

Neuroinflammatory disorders	Musculoskeletal disorders	Skin disorders

 • Cranial nerve disorders, including paralyses/paresis (e.g. Bell's palsy) • Optic neuritis • Multiple sclerosis • Transverse myelitis • Guillain-Barré syndrome, including Miller Fisher syndrome and other variants • Acute disseminated encephalomyelitis, including site specific variants: e.g. non-infectious encephalitis, encephalomyelitis, myelitis, myeloradiculoneuritis • Myasthenia gravis, including Lambert-Eaton myasthenic syndrome • Immune-mediated peripheral neuropathies and plexopathies, (including chronic inflammatory demyelinating polyneuropathy, multifocal motor neuropathy and polyneuropathies associated with monoclonal gammopathy). • Narcolepsy 	
 • Systemic lupus erythematosus and associated conditions • Systemic scleroderma (Systemic sclerosis), including diffuse systemic form and CREST syndrome • Idiopathic inflammatory myopathies, including dermatomyositis • Polymyositis • Antisynthetase syndrome • Rheumatoid arthritis, and associated conditions including juvenile chronic arthritis and Still's disease • Polymyalgia rheumatica • Spondyloarthritis, including ankylosing spondylitis, reactive arthritis (Reiter's Syndrome) and undifferentiated spondyloarthritis • Psoriatic arthropathy • Relapsing polychondritis • Mixed connective tissue disorder 	
 • Psoriasis • Vitiligo • Erythema nodosum • Autoimmune bullous skin diseases (including pemphigus, pemphigoid and dermatitis herpetiformis) • Alopecia areata • Lichen planus • Sweet's syndrome • Localised Scleroderma (Morpheoa)
Vasculitides	Blood disorders	Others

 • Large vessels vasculitis including: giant cell arteritis such as Takayasu's arteritis and temporal arteritis. • Medium sized and/or small vessels vasculitis including: polyarteritis nodosa, Kawasaki's disease, microscopic polyangiitis, Wegener's granulomatosis, Churg-Strauss syndrome (allergic granulomatous angiitis), Buerger's disease (thromboangiitis obliterans), necrotizing vasculitis and anti-neutrophil cytoplasmic antibody (ANCA) positive vasculitis (type unspecified), Henoch-Schonlein purpura, Behcet's syndrome, leukocytoclastic vasculitis. 	
 • Autoimmune hemolytic anemia • Autoimmune thrombocytopenia • Antiphospholipid syndrome • Pernicious anemia • Autoimmune aplastic anaemia • Autoimmune neutropenia • Autoimmune pancytopenia 	
 • Autoimmune glomerulonephritis (including IgA nephropathy, glomerulonephritis rapidly progressive, membranous glomerulonephritis, membranoproliferative glomerulonephritis, and mesangioproliferative glomerulonephritis) • Ocular autoimmune diseases (including autoimmune uveitis and autoimmune retinopathy) • Autoimmune myocarditis/cardiomyopathy • Sarcoidosis • Stevens-Johnson syndrome • Sjögren's syndrome • Idiopathic pulmonary fibrosis • Goodpasture syndrome • Raynaud's phenomenon

Liver disorders	Gastrointestinal disorders	Endocrine disorders

 Autoimmune hepatitis Primary biliary cirrhosis Primary sclerosing cholangitis Autoimmune cholangitis 	
 Inflammatory Bowel disease, including Crohn's disease, ulcerative colitis, microscopic colitis, ulcerative proctitis Celiac disease Autoimmune pancreatitis 	
 Autoimmune thyroiditis (including Hashimoto thyroiditis) Grave's or Basedow's disease Diabetes mellitus type I Addison's disease Polyglandular autoimmune syndrome Autoimmune hypophysitis

When there is enough evidence to make any of the above diagnoses, the AE must be reported as a pIMD. Symptoms, signs or conditions which might (or might not) represent the above diagnoses, should be recorded and reported as SAEs but not as pIMDs until the final or definitive diagnosis has been determined, and alternative diagnoses have been eliminated or shown to be less likely.

In order to facilitate the documentation of pIMDs in the eCRF, a pIMD standard questionnaire and a list of preferred terms and preferred terms codes corresponding to the above diagnoses will be available to investigators at study start.

8.1.5.2. Seizures within 30 or 42 days of vaccination (Amended: 09 August 2016)

All seizures occurring within 30 days of vaccination for vaccine doses administered at 6 and 7.5 months of age (Visits 2 and 3) and within 42 days for vaccine doses administered at 9 months of age (Visit 4) will be reported as SAEs and in *specific eCRF screens*. Key information pertaining to seizures occurring within seven days of vaccination for vaccine doses administered at 6 and 7.5 months of age (Visits 2 and 3) and within 14 days for vaccine doses administered at 9 months of age (Visit 4) will be documented in the eCRF [refer to [Bonhoeffer, 2004](#)].

8.1.5.3. Meningitis (Amended: 09 August 2016)

For the further evaluation of the safety signal of meningitis all the cases occurring during the study will be reported as SAE and medical documentation of the events will be reported in *specific eCRF screens*. Cerebrospinal fluid will be frozen for future testing for infectious agents if applicable (this procedure is fully described in the SPM).

8.2. Detecting and recording adverse events and serious adverse events

8.2.1. Time period for detecting and recording adverse events and serious adverse events

In the Coad and the RTS,S group, all AEs starting after the first vaccine administration (Visit 2) until 42 days following administration of study vaccine at 9 months of age (Visit 4) and AEs starting within 30 days following administration of study vaccine at 27 months of age (Visit 10) must be recorded into the appropriate section of the eCRF, irrespective of intensity or whether or not they are considered vaccination-related.

In the Control group, all AEs starting after the Vitamin A administration (Visit 2) until 42 days following administration of study vaccine at 9 months of age (Visit 4), AEs starting from the day of the first dose of RTS,S/AS01_E (Visit 6) until 30 days after Visit 8 and from the day of the booster dose of RTS,S/AS01_E administered at 30 months of age (Visit 12) until 30 days after the booster dose must be recorded into the appropriate section of the eCRF, irrespective of intensity or whether or not they are considered vaccination-related.

The time period for collecting and recording SAEs will begin at the first receipt of study vaccine and will end 12 months following administration of the last dose of study vaccine (Month 33 for Coad and RTS,S groups and Month 36 for the Control group) for each subject. See Section 8.3 for instructions on reporting of SAEs.

All AEs/SAEs leading to withdrawal from the study will be collected and recorded from the time of the first receipt of study vaccine.

In addition to the above-mentioned reporting requirements and in order to fulfill international reporting obligations, SAEs that are related to study participation (i.e. protocol-mandated procedures, invasive tests, a change from existing therapy) or are related to a concurrent GSK medication/vaccine will be collected and recorded from the time the subject consents to participate in the study until she/he is discharged from the study.

The time period for collecting and recording of AEs of specific interest will begin at the first receipt of study vaccine and will end 12 months following administration of the last dose of study vaccine (Month 33 for Coad and RTS,S groups and Month 36 for the Control group). See section 8.3 for instructions on reporting of AEs of specific interest.

An overview of the protocol-required reporting periods for AEs and SAEs is given in [Table 16](#).

Table 16 Reporting periods for adverse events and serious adverse events (Amended: 09 August 2016)

Visit	1	2	3	4	5	6	7	8	9	10	11	12	13	14	15	
Children age (Months)		6	7.5		9	10	10.5	11.5	12.5	13.5	27	28	30	31	39	42
Study Month		M0		M1.5	M3	M4	M4.5	M5.5	M6.5	M7.5	M21	M22	M24	M25	M33	M36
D-28 to -1	D0	D6	D29	M1.5 +6d M1.5 +29d	M3 +13d	M3 +41d										
Solicited local and general AEs	X ^a	X ^a		X ^a	X ^a		X ^a									
Unsolicited AEs	X ^b	X ^b	X ^b	X ^b	X ^b	X ^b	X ^b	X ^{b,c}	X ^c	X ^c	X ^c	X ^d	X ^d	X ^e	X ^e	
SAEs related to study participation or concurrent GSK medication/vaccine																
SAEs (All, fatal, related to the investigational vaccine)																
AEs of specific interest**																

M: study month; d: day

** AEs of specific interest include seizure (occurring within 30 days post-vaccination for vaccine doses administered at 6 and 7.5 months of age [Visits 2 and 3] or 42 days post-vaccination for vaccine doses administered at 9 months of age [Visit 4]), meningitis and pIMDs.

^a In the Control group, only solicited general AE will be collected. In the Coad and the RTS,S groups, solicited local and general AEs will be collected.^b Unsolicited AEs will be collected from Visit 2 until 42 days after Visit 4 for children in Coad, RTS,S and Control groups.^c Unsolicited AEs will be collected from Visit 6 until 30 days after Visit 8 only for children from the Control group.^d Unsolicited AEs will be collected over a 30-day follow-up period after vaccination only for children from the Coad and the RTS,S groups.^e Unsolicited AEs will be collected over a 30-day follow-up period after vaccination only for children from the Control group.

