- Control: active control (Group receiving the EPI interventions alone [Vitamin A at 6 months and YF vaccine and a combined measles and rubella vaccine at 9 months of age]). Children from this group will receive a 3-dose course (0, 1, 2-month) and a booster dose (17.5 months post Dose 3) of RTS,S/AS01_E from Visit 6 onwards (10.5 months of age) so they can benefit from the same protection as the children from the Coad and the RTS,S groups.
- Vaccination schedules:
 - For the **Coad group**, children will receive Vitamin A and RTS,S/AS01_E vaccine on Day 0 (Visit 2 [6 months of age]), RTS,S/AS01_E alone at Visit 3 (7.5 months of age), co-administration of RTS,S/AS01_E, YF vaccine and a combined measles and rubella vaccine at Visit 4 (9 months of age), and a booster dose of RTS,S/AS01_E at Visit 10 (27 months of age).
 - For the **RTS,S group**, children will receive Vitamin A and RTS,S/AS01_E vaccine on Day 0 (Visit 2 [6 months of age]), RTS,S/AS01_E alone at Visit 3 and 4 (7.5 and 9 months of age), YF vaccine and a combined measles and rubella vaccine at Visit 6 (10.5 months of age), and a booster dose of RTS,S/AS01_E at Visit 10 (27 months of age).
 - For the **Control group**, children will receive Vitamin A on Day 0 (Visit 2 [6 months of age]) and YF vaccine and a combined measles and rubella vaccine at Visit 4 (9 months of age). These children will also receive RTS,S/AS01_E vaccine at Visit 6, 7 and 8 (10.5, 11.5 and 12.5 months of age) and a booster dose of RTS,S/AS01_E vaccine at Visit 12 (30 months of age).
- Treatment allocation: randomized in a 1:1:1 ratio to each study group.
- Blinding: open

Table 3 Blinding of study epoch

Study Epoch	Blinding
Epoch 001	open

- Sampling schedule:
 - For the **Coad group**, blood samples will be taken on Day 0, on the day of co-administration of RTS,S/AS01_E with the YF vaccine and the combined measles

and rubella vaccine (Month 3) and at one month post co-administration (Month 4).

- For the **RTS,S group**, blood samples will be taken on Day 0 and at one month post Dose 3 of RTS,S/AS01_E (Month 4).
- For the **Control group**, blood samples will be taken on Day 0, on the day of administration of the YF vaccine and the combined measles and rubella vaccine (Month 3) and at one month post-vaccination with the YF vaccine and the combined measles and rubella vaccine (Month 4).
- Type of study: self-contained.
- Data collection: Electronic Case Report Form (eCRF).
- Safety monitoring:

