8.3. Reporting of serious adverse events and other events

8.3.1. Prompt reporting of serious adverse events and other events to GSK Biologicals

SAEs that occur in the time period defined in Section 8.2 will be reported promptly to GSK within the timeframes described in [Table 18](#), once the investigator determines that the event meets the protocol definition of a SAE.

AEs of specific interest (pIMDs, meningitis and seizure within 30 or 42 days of vaccination) that occur in the time period defined in Section 8.2 will be reported promptly to GSK within the timeframes described in [Table 18](#), once the investigator determines that the event meets the protocol definition of an AEs of specific interest (pIMDs, meningitis and seizure within 30 or 42 days of vaccination).

Table 18 Timeframes for submitting serious adverse event and other events reports to GSK Biologicals

Type of Event	Initial Reports		Follow-up of Relevant Information on a Previous Report	
	Timeframe	Documents	Timeframe	Documents
SAEs	24 hours*†	electronic Expedited Adverse Events Report	24 hours*	electronic Expedited Adverse Events Report
AEs of specific interest**	24 hours*†	electronic Expedited Adverse Events Report	24 hours*	electronic Expedited Adverse Events Report

* Timeframe allowed after receipt or awareness of the information.

** AEs of specific interest include seizure (occurring within 30 days post-vaccination for vaccine doses administered at 6 and 7.5 months of age [Visits 2 and 3] or 42 days post-vaccination for vaccine doses administered at 9 months of age [Visit 4]), meningitis and pIMDs.

† The investigator will be required to confirm review of the SAE/AEs of specific interest causality by ticking the 'reviewed' box in the electronic Expedited Adverse Events Report within 72 hours of submission of the SAE/AEs of specific interest.

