 - For the Control group, the occurrence of solicited general AEs over a 7-day follow-up period (day of administration and 6 subsequent days) after administration of Vitamin A at 6 months of age (Visit 2).
 - For the Coad and the RTS,S groups, the occurrence of solicited local and general AEs over a 7-day follow-up period (day of vaccination and 6 subsequent days) after dose of study vaccines administered at 7.5 months of age (Visit 3).
 - For the Control group, the occurrence of solicited general AEs over a 7-day follow-up period (day of visit and 6 subsequent days) after Visit 3 (7.5 months of age).
 - For all groups, the occurrence of solicited general and local AEs over a 14-day follow-up period (day of vaccination and 13 subsequent days) after dose of study vaccines administered at 9 months of age (Visit 4).
- Unsolicited AEs.
 - For all groups, the occurrence of unsolicited AEs over a 30-day follow-up period (day of administration and 29 subsequent days) after administration of Vitamin A and study vaccines at 6 months of age (Visit 2).
 - For the Coad and the RTS,S groups, the occurrence of unsolicited AEs over a 30-day follow-up period (day of vaccination and 29 subsequent days) after dose of study vaccines administered at 7.5 months of age (Visit 3).
 - For the Control group, the occurrence of unsolicited AEs over a 30-day follow-up period (day of visit and 29 subsequent days) after Visit 3 (7.5 months of age).
 - For all groups, the occurrence of unsolicited AEs over a 42-day follow-up period (day of vaccination and 41 subsequent days) after dose of study vaccines administered at 9 months of age (Visit 4).

- For the Coad and the RTS,S groups, the occurrence of unsolicited AEs over a 30-day follow-up period (day of vaccination and 29 subsequent days) after the booster dose of study vaccine administered at 27 months of age (Visit 10).
- For the Control group, the occurrence of unsolicited AEs over a 30-day follow-up period (day of vaccination and 29 subsequent days) after dose of study vaccines administered at 10.5, 11.5, 12.5 and 30 months of age (Visit 6, 7, 8 and 12).
- SAEs: all, fatal and related SAEs.
 - The occurrence of SAEs occurring within 30 days (day of vaccination and 29 subsequent days) after each administrations.
 - The occurrence of SAEs from Screening visit (Visit 1) until Month 4.5.
 - The occurrence of SAEs from Screening visit (Visit 1) until study end (Month 33 for Coad and RTS,S groups and Month 36 for the Control group).

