10.5. Cohorts for analyses

10.5.1. Total vaccinated cohort

The total vaccinated cohort (TVC) will include all subjects who received treatment (i.e. receiving at least one dose of study vaccine or Vitamin A). The TVC analysis will be performed per treatment actually administered.

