6.5. Analysis of safety

6.5.1. Analysis of safety planned in the protocol

The primary analysis will be based on the ES.

The percentage of subjects with at least one local AE (solicited and unsolicited), with at least one general AE (solicited and unsolicited) and with any AE during the solicited follow-up period [7 days post Dose 1, post Dose 2 and 14 days post Dose 3] will be tabulated with exact 95% CI after each vaccine dose and overall. The percentage of doses followed by at least one local AE (solicited and unsolicited), by at least one general AE (solicited and unsolicited) and by any AE will be tabulated for the overall vaccination course, with exact 95% CI. Similar tables will be generated for Grade 3 AEs and AEs considered as causally related to vaccination.

The percentage of subjects reporting each individual solicited local and general AE during the solicited follow-up period will be tabulated with exact 95% CI. The percentage of doses followed by each individual solicited local and general AE will be tabulated for each dose and for the overall vaccination course, with exact 95% CI. Similar tables will be generated for Grade 3 AEs, causal events and for fever, temperature in 0.5°C increments.

The proportion of subjects reporting an AE (unsolicited) until 30 days (Days 0-29) post each dose of RTS,S/AS01_E, classified by the Medical Dictionary for Regulatory Activities (MedDRA) preferred term level will be tabulated with exact 95% CI. The proportion of subjects reporting an AE (unsolicited) until 42 days (Days 0-41) after the administration of the YF vaccine and the combined measles and rubella vaccine (restricted to the Coad group and Control group), classified by the MedDRA preferred term level will be tabulated with exact 95% CI. Similar tables will be generated for Grade 3 AEs and AEs considered as causally related to vaccination.

The proportion of subjects reporting an SAE (all, fatal, related) occurring within 30 days (day of vaccination and 29 subsequent days) after each visit where a study product is potentially administered, classified by the MedDRA preferred term level will be tabulated with exact 95% CI.

The proportion of subjects reporting an SAE (all, fatal, related) from Day 0 to Month 4.5 and over the whole study duration (Day 0 to Month 33 for Coad and RTS,S groups and Month 36 for the Control group), classified by the MedDRA preferred term level will be tabulated with exact 95% CI.

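### Protocol 8.2.1 starts Control collection of SAEs, AEs of specific interest and withdrawal events at the first vaccine (Month 3), against Table 6 and the Day 0 analyses, and the SAE endpoint's Screening start is not matched by collection in any group

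*Protocol*

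**What the plan says.** **Collection rule.** Protocol 8.2.1 sets three windows that open at the first vaccine, with no exception for the Control group:

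- SAEs: "The time period for collecting and recording SAEs will begin at the first receipt of study vaccine".
- AEs of specific interest: "The time period for collecting and recording of AEs of specific interest will begin at the first receipt of study vaccine".
- Events leading to withdrawal: "All AEs/SAEs leading to withdrawal from the study will be collected and recorded from the time of the first receipt of study vaccine".

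Protocol 8.3.1 carries this window into the reporting duty: "SAEs that occur in the time period defined in Section 8.2 will be reported promptly to GSK", within the 24 hours of Table 18.

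**Control schedule.** Protocol Section 3 gives Control children "Vitamin A on Day 0 (Visit 2 [6 months of age]) and YF vaccine and a combined measles and rubella vaccine at Visit 4". Table 12 lists no product for them at Visit 3. The cohort definition in Protocol 10.5.1 names Vitamin A apart from vaccine: "receiving at least one dose of study vaccine or Vitamin A".

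**Other places that set a start.** For ordinary AEs, 8.2.1 starts the Control group at Vitamin A, Visit 2. Table 6 marks SAE and specific-interest recording for Control from Visit 2. The pIMD and meningitis endpoints in Protocol 10.2 and SAP 4.2 start at Day 0. The SAE endpoint in the same sections is "The occurrence of SAEs from Screening visit (Visit 1) until Month 4.5". The analysis in SAP 6.5.1 is "The proportion of subjects reporting an SAE (all, fatal, related) from Day 0 to Month 4.5", and Protocol 10.9 also starts at Day 0.

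**The concern.** The endpoints and tables put the three groups side by side from a common start, but 8.2.1 gives the groups different starts. Coad and RTS,S children receive RTS,S/AS01_E at Visit 2, so their window opens on Day 0. A Control child's first vaccine is at Visit 4. A site that applied 8.2.1 and 8.3.1 as written would have no duty under those sections to report a Control SAE or pIMD promptly if it occurred between Visits 2 and 4.

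Any loss would fall on one group only and in one direction: fewer classified events in Control, so that the groups given RTS,S/AS01_E would look worse beside it. Control is the only group without RTS,S/AS01_E up to Month 4.5, so its column is the background against which a reader will judge the other two.

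The Screening start of the SAE endpoint is a second mismatch. It affects all groups alike and does not depend on how Vitamin A is read.

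**Working it through.** **The plan's own figures.** 8.2.1 ends collection 12 months after the last dose. Coad and RTS,S: Month 21 (Visit 10) + 12 = Month 33. Control: Month 24 (Visit 12) + 12 = Month 36. Both match the text, so the closing dates are consistent. Only the opening date is in question.

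**Share of the main window outside the literal Control period.** Inputs: first Control vaccine at Month 3 (Table 6, Table 12); main safety cut-off at Month 4.5, Visit 6 (Protocol 10.11.1).

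- Nominal: (3 − 0) / (4.5 − 0) = 66.7%. For Coad and RTS,S: 0 / 4.5 = 0%.
- In days, with a month of 365.25/12 = 30.44 days and Visit 6 at 42 days after Visit 4: 91.3 / (91.3 + 42) = 68.5%.
- Over the Table 7 windows: Visit 2 falls at age 6 months and Visit 4 at age 9 months, each anywhere within that month, so the gap is about 2 to 4 months (61 to 122 days). Visit 4 to Visit 6 is 28 + 14 = 42 to 42 + 21 = 63 days. Lowest share: 61 / (61 + 63) = 49%. Highest: 122 / (122 + 42) = 74%.
- Against the whole Control follow-up: 3 / 36 = 8.3%.

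**After the fix.** With the start at Visit 2 for every group, as in Table 6, the uncovered share from Day 0 is 0%.

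**Start of Control collection or analysis, place by place.**

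| Place | Control start |
|---|---|
| Protocol 8.2.1, ordinary AEs | Vitamin A, Visit 2 |
| Protocol 8.2.1, SAEs, specific-interest and withdrawal events | first vaccine, Visit 4 |
| Protocol 8.3.1, prompt reporting | as 8.2 |
| Protocol Table 6, SAEs and specific interest | Visit 2 |
| Protocol 10.2 and SAP 4.2, pIMDs and meningitis | Day 0 |
| Protocol 10.2 and SAP 4.2, SAEs | Screening, Visit 1 |
| Protocol 10.9 and SAP 6.5.1, SAEs and specific interest | Day 0 |

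**Screening start.** Screening is 1 to 28 days before Visit 2 (Table 7). The general SAE row is blank at Visit 1 in Tables 4, 5 and 6. From consent, 8.2.1 collects only SAEs related to study participation or to a concurrent GSK product. An endpoint of all SAEs from Screening therefore has no matching collection in any group. The mismatch lies inside each document: Protocol 10.2 against 10.9, and SAP 4.2 against 6.5.1.

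**The case against.** The strongest reply is that the other instructions already cover Control from Day 0. 8.2.1 itself requires all Control AEs after Vitamin A to be recorded whatever their intensity, and a serious event is an AE. Table 6 schedules SAE and specific-interest recording at Visits 2 and 3, so sites that follow it lose nothing. Sections 3 and 5.6.14 require SAEs and AEs of specific interest to be reported to study end in all groups, with no later Control start. Section 8.1.5.3 makes every meningitis case during the study an SAE. Most of this stands, and it limits the likely loss to classification as serious or as a pIMD, and to 24-hour reporting. One qualification: 8.1.1 sends conditions present before the first study vaccination to medical history, which for Control has the same ambiguity.

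A second reply is that study vaccine is used loosely. SAP 6.1.1 glosses first vaccination as Vitamin A for Control. SAP 5.2.1 removes children given no study vaccine from a set that admits children given only Vitamin A. So the literal reading is not the only one. That makes the consequence less certain, but it does not remove the conflict in the text.

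Third, 8.2.2 says Table 16 defines the reporting period. Its SAE and specific-interest rows are blank in the text available here, as in SAP Table 5, probably through PDF conversion. The table may show the intended start, but 8.2.1 would still need to agree with it.

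A reader might go further and infer that the Control SAE rate will be cut to about a third of its true value, that the meningitis comparison is compromised, or that seizures are lost too. The documents do not support these readings. The first needs nothing to be recorded before Month 3, against 8.2.1's own AE rule and Table 6, and neither document gives an SAE risk to work from. The second overlooks 8.1.5.3. On the third, seizures are counted in days after vaccine doses, so Control seizures before Visit 4 are unclear under any start date and are not part of this point.

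**Conclusion.** The point holds as a conflict in the collection rule. Read literally, 8.2.1 leaves a nominal 67% of the Day 0 to Month 4.5 window (about 49% to 74% over the permitted visit windows; 8% of all Control follow-up) outside the Control period for SAEs, AEs of specific interest and withdrawal events, and none of it in the other two groups. These percentages are shares of time, not estimates of bias. They rest on Vitamin A not counting as a study vaccine, which 10.5.1 and the AE rule in 8.2.1 support.

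The exposed part is the descriptive Control column, for SAEs in general and for pIMDs. The stated safety objective compares co-administration with RTS,S/AS01_E alone. Both of those groups start at Visit 2, so it is unaffected. The change should be made because a rule is wrong as written and cheap to correct, not because events are known to have been missed.

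The Screening start of the SAE endpoint is a separate, smaller inconsistency that affects all three groups.

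**What to change.** 1. In Protocol 8.2.1, start all three windows (SAEs, AEs of specific interest, events leading to withdrawal) at Day 0, defined as Visit 2 with the first study vaccine or Vitamin A. This agrees with Table 6, and 8.3.1 then follows without a change of its own. Confirm that the bars in Table 16 and SAP Table 5 show the same start.
2. In Protocol 10.2 and SAP 4.2, start the SAE endpoint at Day 0, as Protocol 10.9 and SAP 6.5.1 already do. List study-related and concurrent-GSK-product SAEs between consent and Day 0 separately.
3. Before the Month 4.5 analysis, check Control events recorded between Visits 2 and 4 for any that met the serious or pIMD definition but were not classified so. If that analysis has already been run, do the check then and report the result.

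Items 1 and 2 are wording only and add no visit, sample or form, because Table 6 already schedules the recording. Item 3 is one review of Control AE records over about three months per child in a planned 233 children.
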